## Data Collection Tools

Data were collected by researchers at a university hospital's blood transfusion center between August 1, 2024, and August 1, 2025. Donors were asked to complete questionnaire forms before and after PAD, a process that took approximately 10-15 minutes.

**Donor Information Form (DIF):** The researchers created the Donor Information Form, which contains a total of 14 questions. The form consists of two sections: socio-demographic characteristics and donor parameters. The first section contains questions about the donors' socio-demographic characteristics (age, gender, education level, occupation, family type, place of residence, and tobacco/alcohol use). The second section contains questions about donor characteristics (blood type information, previous blood donation, and degree of kinship with the recipient).

**Beck Anxiety Scale (BAS):** Measures the frequency of anxiety symptoms experienced by the individual. Beck and colleagues developed it and, it is a 21-item Likert-type self-assessment scale (10). The Turkish validity and reliability study was conducted by Ulusoy and colleagues (11). The sum of the scores is evaluated as follows: 0-7: Minimal anxiety, 8-15: Mild anxiety, 16-25: Moderate anxiety, 26-63: Severe anxiety. The total score is used in the evaluation of the scale, and an increase in the score indicates an increase in the level of anxiety (10).

**Distress Thermometer (DT):** Roth and colleagues developed it in 1998 to measure and evaluate the psychosocial distress experienced by cancer patients (12). Its validity and reliability in Turkish were established by Özalp and colleagues (13). “0” represents no distress, “10” indicates the highest level of distress. The cutoff point is 4 points, and it is recommended that patients with a distress level of 4 points or higher should receive professional support (12).

**Visual Analog Scale (VAS):** The Visual Pain Scale is a safe, valid, and easy-to-use tool for measuring pain repeatedly (14). Its validity and reliability in Turkish were established by Yaray and colleagues (15). “0” on the vertical or horizontal scale denotes no pain, while “10” signifies unbearable pain (14,15).

**Donor Monitoring Chart:** The form prepared by the researchers was used to record vital signs such as temperature, heart rate, blood pressure, respiratory rate, and oxygen saturation before and after the procedure.

## **The Approach Followed in Data Collection and Evaluation**

### **Pre-Implementation Phase**

Prior to commencing the research, a pre-implementation was conducted on a sample representing 10% of the individuals included in the sample scope. This exercise was done to test the clarity and usability of the scales and forms to be used as data collection tools and to evaluate the applicability of using a stress ball and listening to music. Based on the results of the pre-implementation, adjustments were made to the research content, forms, stress ball application, and music listening session, leading to the final form being determined. The data obtained in the pre-implementation phase were not included in the research.

### **Implementation Phase**

The researchers informed donors who met the inclusion criteria about the study's purpose, design, and method and obtained their consent using the Informed Consent Form prepared separately for each group.

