### **Research Population, Sample**

When determining the sample size, the effect size was calculated using results similar to a master's thesis (9). The sample size for the study was calculated using the G-power (v3.1.9.7) program with "effect size = 0.30, alpha = 0.05, power = 0.85, number of groups = 3, and number of measurements = 2" using ANOVA: Fixed effects, omnibus, one-way. The specified calculation yielded a minimum sample size of 93 donors, with 31 donors per group. 14 individuals who declined to participate, 15 who did not meet the inclusion criteria were excluded from the study. Taking all these losses into account, the study was completed with a total of 102 individuals, 34 in each study group.

The study included participants aged  $\geq 18$  and  $\leq 55$  who could read Turkish, had no physical limitations preventing them from squeezing a stress ball, had no psychiatric disorders, vision, hearing, or perception problems, met the platelet apheresis donation criteria according to the institutional protocol, were first-time platelet apheresis donors, voluntarily wished to donate platelets by apheresis, and voluntarily agreed to participate in the study.

Donors who withdrew from PAD, wished to leave the study, developed a reaction during donation, or were unable to complete the procedure due to insufficient blood flow through the catheter were not included in the study.

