## Ensuring Randomization

Platelet apheresis donors were randomly assigned to groups using a stress ball, music listening, and a random number table—a simple random sampling method—to minimize selection bias.

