#### ***Stress Ball Group***

Ten minutes before PAD, DIF, BAS, DT, and VAS were completed as pre-tests during a face-to-face interview, and vital signs were recorded on the Donor Monitoring Chart (DMC). When the PAD procedure began, a stress ball was placed in the palm of one hand. Donors were instructed to squeeze the ball as often as they wished for a total of 30 minutes during the procedure. Five minutes after the donation was completed, the BAS, DT, and VAS were filled out as final tests. Vital signs were recorded on the DMC, and the study was concluded.

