### ***Control group***

Ten minutes before PAD, the DIF, BAS, DT, and VAS were completed as pre-tests during a face-to-face interview, and vital signs were recorded on the DMC. Donors in the control group underwent no intervention during platelet apheresis donation and continued their routine treatment and care. Five minutes after the procedure was completed, the BAS, DT, and VAS were filled out as post-tests. Vital signs were recorded, and the study was concluded.

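### Group-specific consent forms imply that the arm was known no later than signing, and no concealment is described, so the claim to minimise selection bias is not supported

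*Combined protocol and SAP*

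**What the plan says.** All references are to the combined protocol and SAP.

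- **Implementation Phase.** The opening words are "The researchers informed donors who met the inclusion criteria". The sentence goes on to say that donors were told the aim, design and methods of the study, and that the researchers "obtained their consent using the Informed Consent Form prepared separately for each group".
- **Ensuring Randomization.** Assignment is described only as using "a random number table—a simple random sampling method—to minimize selection bias".
- **Research Population, Sample.** Voluntary agreement to take part is one of the inclusion criteria. On losses the section says: "14 individuals who declined to participate, 15 who did not meet the inclusion criteria were excluded from the study". The study finished with 102 donors, 34 per group.
- **Data Collection Tools.** "Data were collected by researchers at a university hospital's blood transfusion center", over the period "between August 1, 2024, and August 1, 2025".
- **Stress Ball Group, Music Listening Group, Control group.** Each group's own procedure opens with the pre-tests. For the stress ball group: "Ten minutes before PAD, DIF, BAS, DT, and VAS were completed as pre-tests during a face-to-face interview". The control group text is nearly the same: "Ten minutes before PAD, the DIF, BAS, DT, and VAS were completed as pre-tests during a face-to-face interview".

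No section names the person who generated or held the sequence, describes a concealment method, or gives the time of assignment.

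**The concern.** Random assignment protects against selection bias only if nobody who decides on entry can know or foresee the next arm. If the recruiter knows the arm, approach and encouragement can vary with it. If the donor knows it, refusal can vary with it. Either would make the three groups differ at entry, and that difference would carry into every between-group comparison used for H1 to H3.

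A form written for one group is a concrete sign that the arm was known during the consent step. This is more than silence about concealment: the text describes a step that needs knowledge of the assignment.

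A second, weaker matter depends on the order of steps. The pre-tests are self-reported and taken face to face. If donors already knew their arm by then, their answers could reflect it. That would affect the baseline comparison and the dependent-groups t-tests, but not directly the post-test comparison between groups.

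**Working it through.** The plan gives no figure to reproduce on this point, so the check sets the sections against each other.

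**Step 1: what the form implies.** To hand over the form for one group, someone must know which group applies. The arm was therefore, on the natural reading, known to the person taking consent by the time of signing. A donor who read the form probably knew it too. The forms themselves are not in the text available for this review, so their exact content is unknown.

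**Step 2: possible orders of events.** The text does not fix the order. Three are possible in principle.

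| Order | Fits a group-specific form? | What could depend on arm |
|---|---|---|
| Assign, approach, agree, sign | Yes | Approach, refusal, withdrawal at signing |
| Approach, agree verbally, assign, sign | Yes | Withdrawal at signing; also approach, if the recruiter could see the list |
| Approach, agree, sign, assign | Not easily | Nothing at entry, if the list was hidden |

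The second order has support in the text. The Implementation Phase section starts from donors who had met the inclusion criteria, and those criteria include voluntary agreement. It is not proven, because the signed form may itself be the agreement. The third order is the one that would support the selection-bias claim, and it is the one that the group-specific form fits least.

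**Step 3: does anything else give protection?** The random number table concerns how the sequence was made, not who could see it. The researchers briefed donors and took consent, and researchers also collected the data; no separate holder of the list is named. So even under the second order, nothing described stops the recruiter from looking ahead.

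**Step 4: what the counts show.** Decliners as a share of decliners plus completers: 14 / (14 + 102) = 14 / 116 = 12.1%. Any donor who consented but is not among the 102 would enlarge the denominator, so 12.1% is a ceiling for the share who declined. The plan does not say whether the 14 had been screened as eligible, which arm they faced, or whether they had been assigned. If all 14 declined before any assignment, refusal contributes no bias. Selective approach by a recruiter would leave no count at all.

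**The case against.** The strongest reply is that the order of events is never stated, and that the literal text favours agreement first. Donors had to have agreed in order to meet the inclusion criteria, and only such donors were given a form. On that reading the arm need not have been known at approach, and the 14 refusals may all precede assignment. This stands, and it limits the point to knowledge no later than signing. It does not remove the point: withdrawal at signing could still depend on arm, and the list is not said to have been hidden.

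Secondly, missing description does not show that bias occurred. This also stands. One could calculate how much a shift in one arm's mean would raise the false-positive rate of the ANOVA, but the result would be the same for a shift from any cause. Nothing in the documents links a particular shift to these forms, so such figures would not measure this defect.

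Thirdly, donors cannot be blinded to a stress ball. That is true but separate. Expectation at post-test would remain even with perfect concealment, whereas hiding the arm until a donor has entered is feasible in an open trial.

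Finally, data collection has ended, so procedural advice comes too late for these donors. That is accepted, and the first part of the fix is confined to reporting.

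**Conclusion.** The point holds in a limited form. The consent procedure implies that the arm was known to the person taking consent, and probably to the donor, no later than signing. With no concealment, list holder or timing described, the stated aim of minimising selection bias is not supported by the procedure as written.

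The size of any bias cannot be determined from the documents, and no bound on it can be given. The conclusion assumes that the form was chosen to match a known assignment, which is the natural reading of the sentence but not an explicit statement.

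A reader might infer more, without support from the documents:

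- *That the arm was known when donors were approached.* Agreement is listed as an entry criterion, so assignment may have followed it.
- *That selection bias occurred.* The documents leave it open; they do not show it.
- *That 12.1% measures the bias.* It is only a ceiling on the share who declined, with arm and timing unknown.
- *That pre-test answers were influenced by arm.* This needs both pre-testing after consent and donor knowledge of the arm, and neither is stated.

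**What to change.** **Completed study.**

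1. State when assignment took place relative to verbal agreement, signed consent and pre-test, and who held the list.
2. Report the 14 refusals by timing, and by arm for any that came after assignment. The 15 ineligible people probably never had an arm; one sentence confirming this is enough.
3. If the arm was known before signed consent, remove or qualify the selection-bias statement under Ensuring Randomization, and state the limitation for the between-group comparisons. If the pre-tests also followed knowledge of the arm, extend the limitation to the baseline comparison and the dependent-groups t-tests.

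This needs no new donor data. Item 2 assumes that a screening log with dates exists; if it does not, say so and keep the limitation statement, which is a text change only.

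**Only if recruitment is reopened or the study repeated.** Use one consent form that describes all three groups. Take consent, complete the BAS, DT and VAS pre-tests, and then reveal the arm by a concealed method, such as sequentially numbered opaque sealed envelopes prepared by someone who does not recruit.

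The cost is an ethics amendment, the envelopes, and a fixed order for steps that already exist. The drawback is that control donors would read about the other arms, although the Implementation Phase section says that donors were already told the study's design.

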#### ***Stress Ball Group***

Ten minutes before PAD, DIF, BAS, DT, and VAS were completed as pre-tests during a face-to-face interview, and vital signs were recorded on the Donor Monitoring Chart (DMC). When the PAD procedure began, a stress ball was placed in the palm of one hand. Donors were instructed to squeeze the ball as often as they wished for a total of 30 minutes during the procedure. Five minutes after the donation was completed, the BAS, DT, and VAS were filled out as final tests. Vital signs were recorded on the DMC, and the study was concluded.

#### ***Music Listening Group***

Ten minutes before PAD, DIF, BAS, DT, and VAS were completed as pre-tests during a face-to-face interview, and vital signs were recorded on the DMC. After the PAD began, donors listened to classical Turkish music modes played through the center's speaker system for 30 minutes. Five minutes after the donation was completed, the BAS, DT, and VAS were filled out as a final test, vital signs were recorded, and the study was concluded.

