# **THE EFFECT OF STRESS BALL and MUSIC ON ANXIETY, STRESS, AND PAIN LEVELS DURING PLATELET APHERESIS DONATION: RANDOMIZED CONTROLLED TRIAL**

## **1. Introduction**

Platelet apheresis transfusion can be used for therapeutic or prophylactic purposes, primarily in oncology and hematology patients (1). Platelet apheresis donors may experience anxiety, stress, and pain due to the need for a wide-lumen vascular access site to ensure adequate blood flow, the complexity of the devices used during the procedure, and the need to keep a needle in the donor's arm for an average of 1 hour. There are numerous approaches, including pharmacological and non-pharmacological methods, to reduce these negative feelings (2). The use of non-pharmacological methods such as listening to music, squeezing a stress ball, watching a movie, using virtual reality glasses, daydreaming, and smelling lavender during invasive procedures has been shown to reduce anxiety, stress, and pain symptoms in individuals (3).

During invasive procedures, stress balls, which are inexpensive and accessible, have been observed to be used as a distraction and attention-grabbing method to reduce anxiety, stress, and pain (4,5,5). Listening to music is another non-pharmacological method that can alleviate anxiety, stress, and pain during invasive procedures. Listening to music before and during invasive procedures has been found to reduce systolic blood pressure, heart rate, and anxiety levels (7,8).

A review of the literature revealed no studies using squeeze ball therapy targeting the sense of touch and music listening targeting the sense of hearing to relieve anxiety, stress, and pain during platelet apheresis donation (PAD). In this context, this study aims to investigate the effects of applying a stress ball, a distraction-attention method, and listening to music, which targets the sense of hearing, on anxiety, stress, and pain levels in platelet apheresis donors, in addition to routine care. It is believed that the data obtained at the end of the study will provide evidence of the effect of stress balls and music listening used during platelet apheresis donation on anxiety, stress, and pain.

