## **2. Materials And Methods**

### **Research Purpose and Design**

This study was a single-center, prospective, randomized controlled trial designed to investigate the effects of using stress balls, a distraction-attention method, and listening to music on anxiety, stress, and pain levels in PAD, in addition to routine care.

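### Music goes out over the centre's speakers with no stated safeguard for the other arms; if sessions overlapped within earshot and music works, music versus control is biased towards zero

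*Combined protocol and SAP*

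**What the plan says.** The Music Listening Group section has donors listening to "classical Turkish music modes played through the center's speaker system for 30 minutes", starting after the donation begins. The Stress Ball Group section describes the ball alone: "Donors were instructed to squeeze the ball as often as they wished for a total of 30 minutes during the procedure". The Control group section states: "Donors in the control group underwent no intervention during platelet apheresis donation and continued their routine treatment and care".

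The setting is one site (Research Purpose and Design: "This study was a single-center, prospective, randomized controlled trial"). Data for all arms come from the same unit over the same year (Data Collection Tools: "Data were collected by researchers at a university hospital's blood transfusion center between August 1, 2024, and August 1, 2025"). Under Ensuring Randomization, donors are allocated by "a random number table—a simple random sampling method—to minimize selection bias", and no allocation by day, session or room is described. The Introduction gives the length of a donation through "the need to keep a needle in the donor's arm for an average of 1 hour".

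The documents mention no headphones, separate room, separate session times, rule on who may be within earshot, or log of when music was playing. They are also silent on whether more than one donor was treated at a time and on how far the speakers carried.

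**The concern.** Music from a loudspeaker is not confined to the donor it is meant for. Allocation is by individual donor and a donation lasts about an hour, so a control or ball donor could be in the room while a music donor's 30 minutes are playing. That control has then received some or all of the music intervention, and that ball donor has received both.

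H1 to H3 all compare the three conditions as if they were distinct. If music leaked into the control arm, a null music result could mean either that music does not work or that controls heard it too. Without a record of exposure, the analysis cannot separate the two.

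**Working it through.** **Inputs from the documents.** Research Population, Sample gives f = 0.30, alpha = 0.05, power = 0.85, three groups, a one-way omnibus ANOVA, a minimum of 93 donors, and 102 completed (34 per arm).

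**The plan's own figure.** For the named test the noncentrality is λ = N·f², with 2 and N − 3 degrees of freedom. At N = 93, λ = 93 × 0.09 = 8.37 and power is 0.72. At N = 102, λ = 102 × 0.09 = 9.18 and power is 0.77. Power of 0.85 needs 126 donors, so 93 is not reproduced. That is a separate matter; here it only means that the starting power is 0.77, not 0.85.

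**Assumptions.**
- Ball and music each improve the outcome by the same d against control. Then f = d·√2/3, so d = 0.30 × 3/√2 = 0.636 SD.
- A share c of controls hears the music. The documents do not give c.
- Each exposed control gets the full music effect. Partial exposure would do less.

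**Music versus control.** The control mean moves by c·d, so the difference becomes d(1 − c):
- c = 5%: 0.636 × 0.95 = 0.60 SD
- c = 10%: 0.636 × 0.90 = 0.57 SD
- c = 20%: 0.636 × 0.80 = 0.51 SD

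**The ball arm.** Two cases bracket it when ball and music work equally well.

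*Case 1: ball donors gain nothing from overheard music.* Every contrast with control scales by (1 − c), so f = 0.30(1 − c).

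*Case 2: ball donors are exposed at the same rate and effects add.* The improvements are c·d for control, d(1 + c) for ball and d for music. Ball versus control is d(1 + c) − c·d = d, which is unchanged. Music versus ball is d − d(1 + c) = −c·d, which is −0.13 SD at c = 20% although the true difference is zero.

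| c | Music − control (SD) | f, case 1 | Power, case 1 | f, case 2 | Power, case 2 |
|---|---|---|---|---|---|
| 0 | 0.64 | 0.300 | 0.77 | 0.300 | 0.77 |
| 5% | 0.60 | 0.285 | 0.72 | 0.293 | 0.74 |
| 10% | 0.57 | 0.270 | 0.67 | 0.286 | 0.72 |
| 20% | 0.51 | 0.240 | 0.56 | 0.275 | 0.69 |

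Power is from the noncentral F at N = 102. Simulation, which also allows for the extra spread when only some donors in an arm are exposed, gives slightly lower values: 0.66 and 0.55 in case 1 at 10% and 20%, and about 0.67 in case 2 at 20%.

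**If the ball works half as well as music.** Then f = 0.30 implies 0.73 SD for music and 0.37 SD for the ball. At c = 20% with additive effects, music versus ball shrinks from 0.37 to 0.22 SD and ball versus control stays at 0.37 SD. If an exposed ball donor instead gains only what is needed to reach the music effect, ball versus control falls from 0.37 to 0.29 SD. The direction for the two contrasts involving the ball therefore depends on how the effects combine; the direction for music versus control does not.

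**The case against.** The strongest reply is that nothing shows any overlap. The documents do not say that two donors were treated at once, and calling the speakers the centre's own tells us who owns them, not how far they carry. The Control group section says plainly that "Donors in the control group underwent no intervention during platelet apheresis donation". A reader might infer that the other arms did hear the music and that all between-arm differences shrank. The documents support neither step: exposure is not recorded either way, and only music versus control has a clear direction of bias.

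A low exposure rate is also plausible. Suppose sessions were spread evenly over 150 to 250 donation days, with starts inside a 4 to 7 hour window and one shared room. About 3 to 7% of controls would then overlap any part of a music session, and 1 to 3% would hear all 30 minutes. That puts the likely loss near the top of the table. The calculation stands as an illustration, but each of its inputs is an assumption, and clustered sessions would raise the rate. It lowers the likely size without closing the gap.

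Finally, data collection is described as finished, so the protocol cannot now be rewritten to say headphones. That is right, and the fix allows for it.

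**Conclusion.** The point holds in conditional form. Speaker delivery in a single-centre, individually randomised trial leaves the control and ball conditions unprotected as far as the documents show. If sessions overlapped within earshot and music works, music versus control is biased towards zero by the factor (1 − c), and the ball arm may be a mixture of ball alone and ball plus music.

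The size cannot be fixed from the documents. At 5% exposure the loss is small: 0.04 SD on music versus control (0.64 to 0.60) and 2 to 5 points of omnibus power. At 20% it is material: 0.13 SD (0.64 to 0.51) and about 8 to 21 points of power. These figures rest on equal ball and music effects at f = 0.30, full effect in every exposed donor, and 34 per arm.

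The point deserves action because individual delivery removes the risk cheaply. It does not show that the trial's comparisons were in fact contaminated.

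**What to change.** **Any further sessions, or a repeat of the trial.** In Music Listening Group, deliver the music by individual headphones instead of the centre's speakers. This needs one or two sets with disposable covers and one sentence of text. The small downside is that the donor hears staff less well.

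**Sessions already run.** Leave the description of what was done as it is, and add the following:
- State the room layout and whether donors of different arms were ever within earshot of a music session. If they were not, one sentence closes the matter.
- If they were, and session dates and times can be recovered (the documents do not say they were recorded), flag each control and ball donor whose session overlapped a music session. Add to Statistical Analysis and Evaluation of Data a sensitivity analysis that excludes them. The cost is the retrieval of times, one extra variable, and a smaller sample in arms of only 34.
- If times cannot be recovered, report possible contamination as a limitation, above all when interpreting a null music-versus-control result.
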